9.2 SAMPLE SIZE DETERMINATION

This is a one arm single-stage Phase II clinical trial. The null hypothesis that the ORR is 0.25 will be tested against the one-sided alternative that the ORR is 0.45. Total of 26 patients yields a

type I error rate of 0.1 when the null hypothesis is true and power of 0.8 when the alternative hypothesis is true.

9.3 POPULATION FOR ANALYSES

All eligible patients who has received any level of the target treatment will be included in the analyses for all preliminary, secondary and safety analysis except for the duration of response analysis. The analysis for duration of response will only include the patients who has responded.

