6. Has a known additional malignancy that is progressing or has required active treatment within the past 3 years. Note: Participants with basal cell carcinoma of the skin, squamous cell carcinoma of the skin, or carcinoma in situ (e.g. breast carcinoma, cervical cancer in situ) that have undergone potentially curative therapy are not excluded
7. Has known active CNS metastases and/or carcinomatous meningitis that requires ongoing treatment or are found to be progressing. Participants with previously treated brain metastases may participate provided they are radiologically stable, i.e. without evidence of progression for at least 4 weeks by repeat imaging (note that the repeat imaging should be performed during study screening), clinically stable and without requirement of steroid treatment for at least 14 days prior to first dose of study treatment.
8. Has severe hypersensitivity (\geq Grade 3) to pembrolizumab or olaparib and/or any of its excipients.
9. Participant must not have impairment of gastrointestinal (GI) function or GI disease that may significantly alter the absorption of the study drugs (e.g., ulcerative diseases, uncontrolled nausea, vomiting, diarrhea, malabsorption syndrome, or small bowel resection).
10. Has active autoimmune disease that has required systemic treatment in the past 2 years (i.e. with use of disease modifying agents, corticosteroids or immunosuppressive drugs). Replacement therapy (eg., thyroxine, insulin, or physiologic corticosteroid replacement therapy for adrenal or pituitary insufficiency, etc.) is not considered a form of systemic treatment.
11. Has a history of (non-infectious) pneumonitis that required steroids or has current pneumonitis.
12. Has an active infection requiring systemic therapy.
13. Has a known history of Human Immunodeficiency Virus (HIV).

14. Hepatitis B (defined as Hepatitis B surface antigen [HBsAg] reactive) or Hepatitis C virus (defined as HCV RNA [qualitative] is detected) infection. Note: no testing for Hepatitis B and Hepatitis C is required unless mandated by local health authority.
15. Has active tuberculosis. Note: no testing for tuberculosis is required unless mandated by local health authority.

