16. Has a history or current evidence of any condition, therapy, or laboratory abnormality that might confound the results of the study, interfere with the subject's ability to cooperate with the requirements of the study, or is not in the best interest of the subject to participate, in the opinion of the treating investigator.
- .
17. Is pregnant or breastfeeding, or expecting to conceive or father children within the projected duration of the study, starting with the screening visit through 120 days after the last dose of trial treatment.

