8.3.4 TIME PERIOD AND FREQUENCY FOR EVENT ASSESSMENT AND FOLLOW-UP

The occurrence of an AE or SAE may come to the attention of study personnel during study visits and interviews of a study participant presenting for medical care, or upon review by a study monitor. All AEs including local and systemic reactions not meeting the criteria for SAEs will be captured on the appropriate CRF. Information to be collected includes event description, time of onset, clinician's assessment of severity, relationship to study product (assessed only by those with the training and authority to make a diagnosis), and time of resolution/ stabilization of the event. All AEs occurring while on study must be documented appropriately regardless of relationship. All AEs will be followed to adequate resolution.

Any medical condition that is present at the time that the participant is screened will be considered as baseline and not reported as an AE. However, if the study participant's condition deteriorates at any time during the study, it will be recorded as an AE. UAPs will be recorded in the data collection system throughout the study.

Changes in the severity of an AE will be documented to allow an assessment of the duration of the event at each level of severity to be performed. AEs characterized as intermittent require documentation of onset and duration of each episode.

The PI will record all reportable events during the designated protocol specified timelines according to Section 8.4.1. SAEs will be followed until resolution or stabilization. At each study visit, the investigator will inquire about the occurrence of AE/SAEs since the last visit.

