9 STATISTICAL CONSIDERATIONS

9.1 STATISTICAL HYPOTHESES

Primary Endpoint:

- Objective Response Rate (ORR per RECIST 1.1) of unirradiated tumors

Secondary Endpoints:

- Overall Survival (OS) from the initiation of therapy to the date of death or to the date of last follow-up.
- Progression Free Survival (PFS) from the initiation of therapy to the date of progression or to the date of last follow-up.
- Duration of response (DoR) defined as the time from documentation of tumor response to disease progression.
- Disease control rate (DCR) defined as the sum of partial (PR), complete response (CR) and SD.
- Treatment-emergent adverse events (AEs), serious adverse events (SAEs)

Exploratory Endpoints:

- Immune changes in tumor tissue and plasma at baseline compared to after combination SBRT/olaparaib and after Olaparib/pembrolizumab
- Assess response based on HRD status, PD-L1 expression, MMR/MSI, and TMB in tumor
- Changes in cytokines, ctDNA in plasma/serum
- Abscopal effect based on irradiated disease site

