9.4 STATISTICAL ANALYSES

9.4.1 GENERAL APPROACH

Summary descriptive statistics will be calculated and presented for all primary, secondary outcomes for all participants, and for stratifications defined by participants demographic characteristics. The demographic characteristics of the participants will be presented with descriptive statistics also. The means, medians and the 95% confidence intervals will be calculated for continuous variables; the frequencies, estimated rates, and the exact 95% confidence intervals will be calculated for the binary and categorical variables.

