9.4.5 SAFETY ANALYSES

Safety Assessments

The safety of Olaparib, SBRT and pembrolizumab will be assessed by evaluating study drug exposure, adverse events, serious adverse events, oncology-related events, all deaths, as well as changes in laboratory determinations and vital sign parameters.

Duration of Study Drug

A summarization of the number of days and/or cycles subjects were exposed to study drug will be provided.

Adverse Events

Analyses of adverse events (and serious adverse events) will include only "treatment-emergent" events, i.e., those that have an onset on or after the day of the first dose of study drug. Analyses will not include those that have an onset greater than 30 days after the last dose of study drug. Treatment emergent adverse events will be summarized by system organ class and preferred term according to the MedDRA adverse event coding dictionary. The percentage of subjects experiencing an adverse event at a given severity, NCI CTCAE toxicity grade, and relationship to study drug will be provided.

Deaths

The number of subject deaths will be summarized (1) for deaths occurring while the subject was still receiving study drug in this study, (2) for deaths occurring off treatment within 30 days after the last dose of study drug, and (3) for all deaths in this study regardless of the number of days after the last dose of study drug. The relatedness of the deaths to the study drugs will also be provided.

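### Section 9.3 applies an eligibility condition to the safety analysis, which can leave a dosed patient later found ineligible out of the AE and SAE tables and conflicts with sections 9.4.1 and 9.4.5

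*Combined protocol and SAP*

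**What the plan says.** Section 9.3 of the combined protocol and SAP states: "All eligible patients who has received any level of the target treatment will be included in the analyses for all preliminary, secondary and safety analysis". *Preliminary* presumably means primary. The one exception is duration of response, which is analysed in responders. The same condition, eligible and treated, therefore governs efficacy and safety. The plan does not define *eligible* for analysis, does not say what happens to a patient found ineligible after dosing, and has no separate safety population.

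Other parts of section 9 describe the safety analysis without that condition:

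- Section 9.4.1: "Summary descriptive statistics will be calculated and presented for all primary, secondary outcomes for all participants". Section 9.1 lists treatment-emergent AEs and SAEs as secondary endpoints, so this sentence covers them.
- Section 9.4.5 on adverse events: "Analyses of adverse events (and serious adverse events) will include only 'treatment-emergent' events". The restriction is on onset time, from the day of first dose to 30 days after the last. Percentages are of *subjects*, with no further definition.
- Section 9.4.5 on deaths gives three summaries. The third is "for all deaths in this study regardless of the number of days after the last dose of study drug".

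On how ineligibility could surface late, exclusion 14 in section 5.2 (hepatitis B or C) adds that "no testing for Hepatitis B and Hepatitis C is required unless mandated by local health authority". Exclusion 15 (active tuberculosis) carries the same kind of note.

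**The concern.** Safety reporting normally covers everyone exposed, because a toxicity is no less real when the patient turns out to have breached an entry criterion. Under 9.3 as worded, an analyst could properly omit such a patient from the AE and SAE tables. Under 9.4.1 or 9.4.5, another analyst could as properly include the same patient. Nothing says which section governs.

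The situation is foreseeable here. Exclusion 14 is defined by a test result (HBsAg reactive or HCV RNA detected), yet the test need not be done before entry. By contrast, exclusion 13 refers to a known history of HIV. Section 8.1 anticipates extra on-study testing for safety reasons and names HIV and hepatitis C as examples. Section 8.3.6.1 says that abnormal liver tests may call for a search for the cause. A liver event during treatment could therefore lead to a test that shows the patient met an exclusion from the start.

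The safety of adding radiotherapy to olaparib is a stated secondary objective. In a trial of about 26 patients, one omitted patient can carry the only severe event of its kind.

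**Working it through.** **1. The plan's own figure.** Section 9.2 gives n = 26, null ORR 0.25, alternative 0.45, one-sided type I error 0.1 and power 0.8. By the exact binomial, rejecting at 10 or more responses gives P(X ≥ 10 | 26, 0.25) = 0.0909 and P(X ≥ 10 | 26, 0.45) = 0.8064. The sample size reproduces. Nothing below depends on it, and changing the safety set does not alter it.

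**2. The sections side by side.** Take a dosed patient with a severe liver event during treatment who is then found HBsAg reactive.

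| Section | Who or what is covered | Eligibility condition | This patient |
|---|---|---|---|
| 9.3 | Eligible treated patients, efficacy and safety | Yes | Out, on a literal reading |
| 9.4.1 | All participants, secondary outcomes (includes AEs/SAEs) | No | In |
| 9.4.5, AEs | Events by onset time | No | In |
| 9.4.5, deaths, third summary | All deaths | No | Counted, if the patient dies |
| 8.3.1, collection | All AEs from treatment to 30 days after | No | Data collected |

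**3. Effect on a percentage.** Let n be treated, x those with the event, k left out as ineligible, and e those among the k with the event. The reported rate moves from x/n to (x − e)/(n − k). The count x − e can only fall or stay the same. The rate falls when (x − e)/(n − k) < x/n, which rearranges to e/k > x/n. That means the excluded patients had the event more often than the treated group as a whole, and so more often than those kept.

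With n = 26 (section 9.2) and illustrative values of x and k:

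| x/26 | k | All k had the event | None had it |
|---|---|---|---|
| 1/26 = 3.8% | 1 | 0/25 = 0% | 1/25 = 4.0% |
| 3/26 = 11.5% | 1 | 2/25 = 8.0% | 3/25 = 12.0% |
| 5/26 = 19.2% | 1 | 4/25 = 16.0% | 5/25 = 20.0% |
| 5/26 = 19.2% | 2 | 3/24 = 12.5% | 5/24 = 20.8% |
| 5/26 = 19.2% | 3 | 2/23 = 8.7% | 5/23 = 21.7% |

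**4. The rare-event case with limits.** 1/26 has an exact 95% interval of 0.1% to 19.6%. 0/25 has an upper limit of 1 − 0.025^(1/25) = 13.7%. The table would go from showing one such event to showing none.

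**5. How often this would happen.** The documents give no rate. If 2%, 5% or 10% of dosed patients were later found ineligible (assumed values), the chance of at least one among 26 is 1 − (1 − p)^26 = 40.9%, 73.6% or 93.5%. This is the chance of any such patient, not of losing a severe event.

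**6. Denominator.** Section 4.4 ties the 26 to patients evaluable after both treatment phases, and the synopsis allows up to 32 enrolled. The number treated could exceed 26, which would make each step slightly smaller: 1/32 = 3.1% becomes 0/31.

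**The case against.** The best defence is that 9.3 is a sentence of inclusion and deletes nobody. Where that section means to restrict, for duration of response, it says that only responders are included. Section 5.1 treats eligibility as an entry decision, so the word may mean no more than having passed screening. This has force, because exclusion of a dosed patient is an inference from one undefined word. It does not remove the problem. On that reading the word adds nothing to the safety rule, and 9.3 still differs from 9.4.1 and 9.4.5.

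Three stronger readings are tempting and are not supported:

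- *A reader might infer that deaths are dropped.* Section 9.4.5 calls for a count of all deaths, so the most that can be said is that the two sections disagree.
- *A reader might infer that toxicity is understated.* That holds for counts in the sense that they cannot rise. Percentages lose both numerator and denominator and can go up. It is plausible that a serious event prompts the check that reveals ineligibility, but the documents do not establish it.
- *A reader might see a contradiction with section 8.3.4*, which says "All AEs occurring while on study must be documented appropriately regardless of relationship". That sentence governs documentation, and recording every event is compatible with analysing a subset. SAE reporting and committee review (8.3.6, 10.1.5) are likewise untouched by 9.3.

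Exclusion 16, "any condition, therapy, or laboratory abnormality that might confound the results of the study", might also be offered as a source of late ineligibility. It rests on the treating investigator's opinion and no later re-adjudication is described, so it adds little. The untested infections carry the argument.

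**Conclusion.** The point holds as an internal conflict with a possible wrong result. Section 9.3 puts an eligibility condition on the safety analysis, no all-treated safety set exists, and sections 9.4.1 and 9.4.5 imply a wider group. Followed literally, 9.3 can leave a dosed patient out of the AE and SAE tables.

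The effect is small per patient, at most about 4 percentage points at 26 treated, but it can remove the only event of a kind. Its direction for percentages is open, and its frequency is unknown. The conclusion rests on reading *eligible* in its ordinary sense and on the possibility that an unscreened exclusion comes to light after dosing. It does not rest on any assumed rate. The change should be made before analysis.

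**What to change.** In section 9.3, separate the two populations:

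*The safety population is every patient who received at least one fraction of SBRT or at least one dose of olaparib or pembrolizumab, regardless of eligibility. It is used for all analyses in section 9.4.5.*

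Keep any eligibility condition to the efficacy set, and state there what *eligible* means and when it is judged. Reword section 9.4.1 so that it refers to these populations, and name the safety population as the denominator for the percentages in 9.4.5. List every treated patient later found ineligible, with the reason.

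The cost is a sentence, the matching edits and a listing. No further patients, visits or data are needed, because AEs are already collected on everyone treated, and the sample size is unaffected. Reported toxicity may change slightly, in either direction.

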9.4 STATISTICAL ANALYSES

9.4.1 GENERAL APPROACH

Summary descriptive statistics will be calculated and presented for all primary, secondary outcomes for all participants, and for stratifications defined by participants demographic characteristics. The demographic characteristics of the participants will be presented with descriptive statistics also. The means, medians and the 95% confidence intervals will be calculated for continuous variables; the frequencies, estimated rates, and the exact 95% confidence intervals will be calculated for the binary and categorical variables.

9.4.2 ANALYSIS OF THE PRIMARY EFFICACY ENDPOINT(S)

One-sided proportion test will be conducted for the ORR, with significant level 0.1. The cumulative frequency, estimated proportion and the exact 95% confidence interval will be reported.

9.4.3 ANALYSIS OF THE SECONDARY ENDPOINT(S)

No formal hypothesis tests will be conducted for the secondary endpoints. Descriptive summarize statistics will be presented. The cumulative frequency, estimated proportion and the exact 95% confidence interval will be reported for the Disease control rate. For OS, PFS and DOR, the survival probability (Kaplan-Meier survival curve) will be calculated by the Kaplan-Meier method, the survival curve and the median survival time will be reported with the corresponding 2-sided 95% Brookmeyer-Crowley's Confidence Interval if feasible.

9.4.4 ANALYSIS OF THE EXPLORATORY ENDPOINTS

Exploratory immune analyses will be conducted to evaluate anti-tumor immune responses. The exploratory objectives are intended to collect data for use in planning future scientific investigations or clinical research. Each of the exploratory analyses are expected to be performed only using descriptive techniques, reporting descriptive statistics including confidence intervals when appropriate. Any statistical tests performed for evaluation of exploratory objectives will be done without formal adjustment for multiple comparisons, but in the context of the number of tests performed. A subject will be considered evaluable for immune response if they receive at least one dose of treatment, SBRT + Olaparib and Olaparib + Pembrolizumab,. The magnitude of immune responses will be described.

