^b All patients with clinically significant abnormal laboratory results at treatment completion or study drug discontinuation (EOT) visit are to be followed until the results return to normal (or patient's baseline), or until a valid reason, other than a drug- related effect, is identified. Patients with an unresolved AE or SAE event at treatment completion or study drug discontinuation will be contacted by the investigator or his or her designee to determine the status of the event until the event is resolved or stabilized, the patient is lost to follow up, or it has been determined that the study treatment or participation is not the cause of the event. If the post-trial visit occurs less than 30 days after the last dose of study treatment, a subsequent follow-up phone call should be made at 30 days post the last dose of study treatment to determine if any adverse events have occurred since the post-trial clinic visit

^c Pregnancy test on blood or urine samples will be performed for pre-menopausal women of childbearing potential one within 28 days prior to the start of study treatment and the other on Day 1 of the study prior to commencing treatment. Tests will be performed by the hospital's local laboratory. If results are positive the patient is ineligible/must be discontinued from the study. In the event of a suspected pregnancy during the study, the test should be repeated.

^d First biopsy and correlative bloodwork to be collected prior to C1D1 (within 14 days of starting therapy). For baseline biopsy only, available archived tumor tissue of a metastatic tumor collected up to 28 days prior to registration is acceptable. Second biopsy and correlative bloodwork to be collected within 5 days prior to C2D1, before treatment with olaparib/pembrolizumab. Third biopsy and correlative bloodwork to be collected within 5 days prior to C4D1, before starting treatment with olaparib/pembrolizumab. Correlative bloodwork only within 5 days of EOT.

^e Cycle 2 Day 1 should start within two weeks of completing combination olaparib and radiation.

^f Vital signs should include temperature, pulse, respiratory rate, weight and blood pressure. Height will be measured at screening only.

^g Perform on Day 1 of every cycle starting from Cycle 2 and at EOT

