6 STUDY INTERVENTION

6.1 STUDY INTERVENTION(S) ADMINISTRATION

Potential trial patients will be pre-identified at participating centers into two cohorts:

- (1) germline or somatic deleterious mutation involving genes critical to the DNA repair through homologous recombination deficiency (HRD), as demonstrated by Next-generation DNA sequencing in a CLIA certified, CAP tested and bioinformatics-validated testing lab prior to enrollment. This could include, but not be limited to one of the following genes: *ARID1A*, *ATM*, *ATR*, *MRE11A*, *NBN*, *PTEN*, *RAD50/51/51B*, *BARD1*, *BLM*, *BRCA1*, *BRCA2*, *BRIP1*, *FANCA/C/D2/E/F/G/L*, *PALB2*, *WRN*, *CHEK2*, *CHEK1*, *BAP1*, *FAM175A*, *SLX4*, *MLL2* or *XRCC* and
- (2) no evidence of HR deficiency.

If a pathogenic mutation in the HR pathway is confirmed and not listed above, the study PI will determine if the patient is eligible based on available clinical or pre-clinical literature.

[figure not shown]
The determination of a deleterious mutation must be supported in the documentation included in the testing, and should include clinical, or pre-clinical literature to support the finding that a

specific mutation results in impaired function of the gene, and thus impaired DNA repair through homologous recombination. Mutations and deletions will be evaluated against the Human Gene Mutation database and other online databases (ClinVar, Breast Cancer Information Core, PubMed) to evaluate the functional relevance, and to make a determination on the likelihood of the mutation resulting in defective homologous recombination-dependent DNA repair. Variants of unknown significance will not be eligible.

The testing may have been done at any time prior to enrollment.

Starting C1D1, olaparib 200mg PO BID will be given concurrently with radiation (25 Gy in 5 fractions). Each cycle is 21 days. Starting on C2D1, Pembrolizumab 200mg IV will be administered on Day 1 every 3 weeks with olaparib 300mg PO BID (12 hours apart). There is no specification regarding the sequence in which the drugs should be given on days when they are administered together. For Cycle 1, patients will be evaluated weekly for 3 weeks with blood tests, clinic visits, and physical exams. Starting Cycle 2, patient will be evaluated every 3 weeks on Day 1 of each cycle.

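### Section 9.4.4 makes the baseline versus post-SBRT/olaparib immune contrast depend on a later olaparib + pembrolizumab dose, so a patient sampled before C2D1 but never given that combination is non-evaluable for it

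*Combined protocol and SAP*

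**What the plan says.** The exploratory endpoint in section 9.1 is "Immune changes in tumor tissue and plasma at baseline compared to after combination SBRT/olaparaib and after Olaparib/pembrolizumab". It holds two comparisons with baseline: one after SBRT/olaparib and one after olaparib/pembrolizumab.

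Footnote d of the schedule of events (section 1.3) fixes the samples:

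- Baseline: "First biopsy and correlative bloodwork to be collected prior to C1D1 (within 14 days of starting therapy").
- After SBRT/olaparib: "Second biopsy and correlative bloodwork to be collected within 5 days prior to C2D1, before treatment with olaparib/pembrolizumab".
- After olaparib/pembrolizumab: "Third biopsy and correlative bloodwork to be collected within 5 days prior to C4D1".
- End of treatment: "Correlative bloodwork only within 5 days of EOT".

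Section 6.1 sets the start of the combination: "Starting on C2D1, Pembrolizumab 200mg IV will be administered on Day 1 every 3 weeks with olaparib 300mg PO BID".

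Section 9.4.4 gives a single rule for the immune analyses. A subject is "evaluable for immune response if they receive at least one dose of treatment, SBRT + Olaparib and Olaparib + Pembrolizumab". It does not separate the two contrasts and does not ask for any sample. Section 9.3 has a broader population, patients who received any amount of the treatment, but these are "included in the analyses for all preliminary, secondary and safety analysis except for the duration of response analysis". The exploratory analyses are not named there, so the rule in 9.4.4 stands.

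**The concern.** For the comparison after olaparib/pembrolizumab, requiring both parts of the regimen is reasonable. For the comparison after SBRT/olaparib it is not needed. Exposure to SBRT and olaparib, the baseline sample and the second sample are all in place before pembrolizumab is given. Whether the patient later receives the combination cannot change either measurement, yet it decides whether the pair counts.

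Two things are at stake. First, a complete pair, often including an invasive biopsy, drops out of the contrast. Second, inclusion depends on an event after the measurement. If patients who are sampled and then fail to start Cycle 2 differ in their immune change from those who do start, the summary is shifted. Section 2.2 presents induction radiation with PARP inhibition as a way of priming the tumor, and this contrast is the direct tissue and blood description of that step. Section 9.4.4 says the exploratory results are meant for planning later research, so they should describe every patient who had the induction and has a pair.

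**Working it through.** **The plan's own figure.** The immune analysis has no stated sample size or precision. The only statistical figure is the 26 patients for the ORR test in section 9.2 (0.25 against 0.45, one-sided 0.1, power 0.8). It reproduces with the exact binomial and success at 10 or more responders of 26: P(X ≥ 10 | 0.25) = 0.091 and P(X ≥ 10 | 0.45) = 0.806. The present point does not depend on it.

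**Samples set against the rule.**

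| Item | Timing | Relative to first olaparib + pembrolizumab dose |
|---|---|---|
| Baseline tissue and blood | before C1D1 | before |
| SBRT + olaparib | from C1D1 | before |
| Second tissue and blood | within 5 days before C2D1 | before |
| First olaparib + pembrolizumab dose | C2D1 | the exposure that 9.4.4 requires |
| Third tissue and blood | within 5 days before C4D1 | after |

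Both samples of the first contrast lie above the line that decides evaluability.

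**Who is affected.** Only a patient who has a baseline sample, has a second sample in the 5-day window, and then never receives the combination. This can happen. The laboratory footnote in section 1.3 lets pre-dose tests after Cycle 1 be drawn up to 72 hours before dosing and requires acceptable results before each dose, so a biopsy can precede a result that holds up C2D1. Toxicity, clinical deterioration or withdrawal can also intervene. A delay alone does not cost the pair; never starting does.

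**Size.** Let q be the proportion of 26 patients who are sampled before C2D1 and then not given the combination. The documents give no value for q; 0-20% is an assumption. Suppose that all 26 have a pair and that the SD of the paired change is the same with or without the excluded patients. Then:

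- pairs lost = 26 × q
- ratio of standard errors = √(26 / (26 × (1 − q))) = 1/√(1 − q)

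| q | Pairs lost | Pairs left | SE ratio |
|---|---|---|---|
| 0% | 0 | 26 | 1.00 |
| 5% | 1.3 | 24.7 | 1.03 |
| 10% | 2.6 | 23.4 | 1.05 |
| 15% | 3.9 | 22.1 | 1.08 |
| 20% | 5.2 | 20.8 | 1.12 |

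At 20%, a cohort of 13 keeps 13 × 0.8 = 10.4 pairs on average. Where biopsies are missing, fewer than 26 tissue pairs exist and the number lost falls in proportion.

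**The case against.** A single population that received the whole regimen can be defended. The exploratory objective concerns SBRT, olaparib and pembrolizumab together, and using the same patients for both contrasts keeps the two changes comparable. That is a fair reason to show such a summary. It is not a reason to make it the only one, and showing both answers the point.

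The sentence in 9.4.4 is loosely punctuated, and it defines who is evaluable without saying that other data go unreported. Exclusion is therefore the consequence of the rule, not its stated text. Requiring both parts is still the natural reading, and section 4.4 uses the same two-part condition for the primary endpoint. If either part were enough, patients without pembrolizumab would count for the contrast after pembrolizumab. One rule cannot suit both contrasts.

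A reader might infer more than the documents support:

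- **That 10-20% of all treated patients, some 3 to 6 pairs, would be lost.** This treats everyone who fails to start Cycle 2 as having a complete pair. The second sample is tied to C2D1, so patients who stop early in Cycle 1 will usually have no pair to lose. The first on-study scan is scheduled at 9 weeks, so no planned imaging between the second sample and C2D1 would detect progression. Sections 5.1 and 6.1 also allow biopsies to be omitted.
- **That about 29 to 32 patients would be treated to obtain 26 who start Cycle 2.** The synopsis gives 32 as an enrollment maximum that allows for screen failures, not as a plan to replace treated patients.
- **That the rule is what stops the contrast describing everyone given SBRT and olaparib.** Most of that selection comes from the schedule: any second sample requires the patient to get close to C2D1. The rule adds only the patients sampled and then not dosed, and a corrected rule would still leave out those never sampled.

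The absence of a sample requirement is a smaller matter. A dosed patient without a pair adds nothing to a paired change, so only the reported count of evaluable patients is affected.

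**Conclusion.** The point holds as a mis-specified rule for one exploratory contrast. As written, inclusion in the baseline versus post-SBRT/olaparib comparison depends on a dose given after both measurements, and no other section overrides this. The effect is small and its size is unknown: possibly zero, and 0 to about 5 pairs with a standard error up to 12% larger under the assumed 0-20% of 26. The added selection is confined to patients sampled before C2D1 and never given olaparib + pembrolizumab; the documents do not allow its direction or size to be stated. The immune analyses are expected to be descriptive, and the ORR test, the sample size and the safety analyses do not change. It is a minor correction, worth making because it costs almost nothing and settles in advance which pairs count.

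**What to change.** In section 9.4.4, replace the single rule with one for each contrast:

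- **After SBRT/olaparib:** any SBRT + olaparib received, plus a baseline sample and a pre-C2D1 sample.
- **After olaparib/pembrolizumab:** at least one dose of that combination, plus a baseline sample and a pre-C4D1 sample. End-of-treatment blood should not stand in for a missing pre-C4D1 sample, because it is taken at a different and variable time.

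Report the number of pairs for each contrast and each assay. Optionally, also show the first contrast in patients who received both parts, so that the two changes can be compared in a common population.

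The cost is one or two sentences and a different N for the two contrasts, which the tables must show. No extra patients, samples or visits are needed.
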